1. PURPOSE OF THE STUDY

a. Brief Summary

This is a comparison study of two types of scanners: we want to compare the results of the standard-of-care PET/CT scanner with a new digital PET/CT scanner and we plan to do this on the same day using a single dose of a radioactive drug that is FDA-approved to be used for the PET/CT scan (FDG, NaF, DOTATATE) or radioactive drugs not FDA-approved but for which we hold INDs (Ga68 PSMA and Ga68 RM2 used in prostate cancer).

We hope to learn if the lesions seen using one standard of care scanner (PET/CT) are also seen using the novel scanner (digital PET/CT).

The goal of this study is to acquire matched sets of imaging in order to compare the standard PET/CT and digital PET/CT.

b. Objectives

Understanding the imaging characteristics of these two scanners can potentially improve the patient care, improving the image quality, by scanning the patients most suitable for the individual scanner. Understanding what patients will benefit from digital PET/CT instead of standard PET/CT will have the potential to improve patient care.

c. Rationale for Research in Humans

The scanners are designed for detection of disease in human subjects; therefore, comparing the image quality of the two requires human participants.

2. STUDY PROCEDURES

a. Procedures

Patients who are referred to Nuclear Medicine and are scheduled to undergo standard or research (68Ga PSMA or 68Ga RM2) PET/CT on the Discovery 600 or 690 scanner will be asked to have the scan repeated on the Discovery MI scanner. Conversely, patients

who are referred to Nuclear Medicine and are scheduled to undergo standard or research (68Ga PSMA or 68Ga RM2) PET/CT on the Discovery MI scanner will be asked to have the scan repeated on the Discovery 600 or 690 scanner. There will be a single injection of the PET radiopharmaceutical followed by the standard PET/CT scan and immediately after by the digital PET/CT scan. A very small amount of radiation (3 mSv) will be given by the attenuation correction CT scan in the second PET/CT.

PET/CT images will be obtained using the GE PET/CT 600 or 690 scanners (GE Healthcare) per standard oncologic protocols. In brief, PET/CT images will be acquired in 3D mode at 45-60 minutes after injection of the radiopharmaceutical. We plan to enroll 100 patients per year for both SOC and research tracers, for 3 years (total of 300 patients). The PET emission scan is corrected using segmented attenuation data of the CT scan. ToF will be used for patients with $BMI > 25$ (on the 690 system only). The PET images are reconstructed both with a standard iterative algorithm (OSEM, two iterative steps, 28 subsets), as well as a regularized reconstruction algorithm provided by GE Healthcare. All images are reformatted into axial, coronal, and sagittal views and viewed with the software available in the Nuclear Medicine and Molecular Imaging Clinic (MIM Vista).

Immediately after completion of the standard PET/CT exam, the patients will be transferred to the adjacent digital PET/CT suite and undergo the second PET/CT image acquisition with the least delay. In brief, PET/CT images will be acquired in 3D mode. ToF is standard on the digital PET/CT system. Data driven gating will be acquired according to the vendor's protocol (once commercially available). The PET emission scan is corrected using segmented attenuation data of the CT scan. The PET images are reconstructed both with a standard iterative algorithm (OSEM, two iterative steps, 28 subsets), as well as a regularized reconstruction algorithm (Q.Clear®) provided by GE Healthcare. All images are reformatted into axial, coronal, and sagittal views and viewed with the software available in the Nuclear Medicine and Molecular Imaging Clinic (MIM Vista).

The above sequences will be done as well if the digital PET/CT is done first, followed by Discovery 600 or 690.

b. Procedure Risks

No significant risks are associated with the imaging procedures involved.

c. Use of Deception in the Study

Deception will not be used in this study.

d. Use of Audio and Video Recordings

Audio and video recording will not be used in this study.

e. Alternative Procedures or Courses of Treatment

The participant is already referred for standard or research (68Ga PSMA or 68Ga RM2) PET/CT. No other alternate procedures are available. The subject can choose not to participate in the project.

f. Will it be possible to continue the more (most) appropriate therapy for the participant(s) after the conclusion of the study?

No therapy is used in this study. The protocol will not affect any therapy the patient might receive outside this research.

g. Study Endpoint(s)

No alternative treatments are proposed.

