Immediately after completion of the standard PET/CT the subject will undergo a study scan using the Discovery PET/CT system. Similarly, if Discovery PET/CT will be used first, scan will be acquired immediately after using standard PET/CT.

Collection of the study PET/CT imaging data shall be completed up to 1 hour after completion of the standard PET/CT scan. First a CT will be done for attenuation correction. This will be followed by emission PET scan over the same regions.

ii. Total number of times each procedure will be performed (typical study participant)

Once.

- iii. Setup and techniques to support dose modeling
 - First PET/CT: CT as ordered by referring physician, followed by emission PET
 - Second PET/CT: CT for attenuation correction, followed by emission PET
- iv. FDA status of the machine and information on dose modeling (if procedure is not well-established)

The digital PET/CT is now FDA-approved

d. Radiation Machines – Therapeutic Procedures

- i. Area treated, dose per fraction/number of fractions, performed as part of normal clinical management or due to research participation (well-established procedures)
N/A
- ii. FDA status of the machine, basis for dosimetry, area treated, dose per fraction and number of fractions (if procedure is not well-established)
N/A

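### Scan order follows the booked scanner, and the only planned test takes no account of order, so the scanner difference may include a second-scan effect of unknown size and sign

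*Protocol*

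**What the plan says.** Protocol section 2.a sends patients booked on the Discovery 600 or 690 to the Discovery MI for a repeat scan, and in the other direction: "PET/CT on the Discovery MI scanner will be asked to have the scan repeated on the Discovery 600 or 690 scanner". Two later sentences confirm that both orders occur: "The above sequences will be done as well if the digital PET/CT is done first, followed by Discovery 600 or 690" (section 2.a) and "Similarly, if Discovery PET/CT will be used first, scan will be acquired immediately after using standard PET/CT" (section 4.c.i). Nothing in either document randomises, alternates or balances order, or gives the share of patients in each.

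There is one injection, so the second scan is always the later one. The section 2.a injection sentence covers one order only: "There will be a single injection of the PET radiopharmaceutical followed by the standard PET/CT scan and immediately after by the digital PET/CT scan". The time limit in section 4.c.i is also worded for that order: "Collection of the study PET/CT imaging data shall be completed up to 1 hour after completion of the standard PET/CT scan". Section 4.c.iii distinguishes the CT by position: "First PET/CT: CT as ordered by referring physician, followed by emission PET", then a CT for attenuation correction at the second scan.

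The SAP gives one test, a two-tailed paired t-test of Likert image-quality score between standard and digital scanners, significant at P<0.05. It mentions no order term, no stratification and no results by order. That all pairs are analysed together is inferred from this silence.

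**The concern.** Pairing removes differences between patients. It does not remove differences between first and second position within a patient. Remaining activity and uptake time differ by position for everyone, and the CT may differ for some. If one order is much commoner than the other, whatever position does to the score goes mostly to one scanner.

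Comparing the scanners is the purpose of the study, and this is its only planned test. A significant result could partly reflect order, or a real scanner difference could be diluted. With nothing reported by order, a reader could not tell whether either had happened.

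**Working it through.** **The plan's own figure.** Section 2.a states "We plan to enroll 100 patients per year for both SOC and research tracers, for 3 years (total of 300 patients"): 100 × 3 = 300, which reproduces. It is an accrual target. Neither document gives an SD, target difference, power, order split or number of pairs analysed, so those inputs below are assumptions.

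**Model.** Let T be the true digital-minus-standard difference, g the second-minus-first effect in Likert points, and p the share scanned standard-first. Assume T is the same in both booking groups.

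- Standard-first patients (digital second): mean difference T + g.
- Digital-first patients (standard second): mean difference T − g.
- All pairs together: p(T + g) + (1 − p)(T − g) = T + (2p − 1)g.

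The overall mean is free of order only if p = 0.5 or g = 0. The documents secure neither.

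**Chance of P<0.05 when T = 0.** Rejection = Φ(−1.96 + d) + Φ(−1.96 − d), with d = (2p − 1)·g·√n / SD. For p = 0.8, g = 0.2, SD 1.0, n = 300: d = 0.6 × 0.2 × 17.32 = 2.08, giving 54.7%. With SD 1.0 throughout:

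| p | g | n = 300 | n = 100 | n = 50 |
|---|---|---|---|---|
| 0.8 | 0.2 | 54.7% | 22.4% | 13.6% |
| 0.8 | 0.1 | 18.0% | 9.2% | 7.1% |
| 0.8 | 0.05 | 8.1% | 6.0% | 5.5% |
| 0.6 | 0.2 | 10.7% | 6.9% | 5.9% |
| 0.5 | any | about 5% | about 5% | about 5% |

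At p = 0.8, g = 0.2, n = 100, the rate is 40.3% with SD 0.7 and 15.2% with SD 1.3.

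**Dilution.** With T = 0.20, g = −0.2, p = 0.8, the overall mean is 0.20 + 0.6 × (−0.2) = 0.08. Power at SD 1.0 and n = 300/100/50 is 28/13/9%, against 79/36/20% for the order-balanced estimate below.

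**Order-balanced estimate.** The unweighted mean of the two order-specific means is [(T + g) + (T − g)]/2 = T. Its SE is (SD/2)·√(1/n1 + 1/n2), which is the pooled SE times 1/√(4p(1 − p)): 1.02 at 60:40, 1.25 at 80:20, 1.67 at 90:10. A simulation with T = 0, p = 0.8, g = 0.2, SD 1.0 and 20,000 replicates gave rejection rates at n = 300/100/50 of 53.8/21.3/12.6% for the pooled t-test and 4.7/5.2/5.1% for the order-balanced estimate (t on n − 2 df).

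**Where pooling is better.** The pooled estimate has the lower mean squared error when |g| < SD/√(4np(1 − p)): 0.072/0.125/0.177 at p = 0.8, SD 1.0, n = 300/100/50.

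**If the scanner effect differs by booking group.** Take 0.3 in standard-first and 0.1 in digital-first patients, with p = 0.8. The patient-weighted scanner effect is 0.8 × 0.3 + 0.2 × 0.1 = 0.26, but the order-balanced estimate targets 0.20. The gap between the order-specific means is (0.3 − 0.1) + 2g, so its two sources cannot be separated.

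**The case against.** The strongest reply is that no bias has been demonstrated. Both p and g are invented, the larger rates all use p = 0.8, and the protocol recruits both booking groups and limits the gap: "the patients will be transferred to the adjacent digital PET/CT suite and undergo the second PET/CT image acquisition with the least delay". At 60:40 the distortion is small. All of this stands, and it is why the claim stops at possible bias.

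Second, the order-balanced estimate replaces one assumption with another: order was not randomised, so it needs a similar scanner effect in both booking groups. This also stands. It is a reason to show both estimates, not to omit the results by order.

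Third, a rule that discounts the t-test whenever the balanced result is non-significant would misfire. With a real effect of 0.20, no order effect, p = 0.8 and SD 1.0, the balanced result was non-significant in 16/39/46% of significant pooled results at n = 300/100/50 (40,000 simulated replicates). Such a rule should not be used.

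Stronger readings are tempting but unsupported:

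- A reader might infer from the injection sentence that everyone was scanned standard-first, so that scanner and order cannot be separated at all. Sections 2.a and 4.c.i explicitly provide for the reverse order.
- A reader might infer that the CT differs by position in every patient. The first CT is whatever was ordered, which need not differ from an attenuation-correction CT, and the SAP does not say whether the score covers CT appearance.
- A reader might try to size the effect from radioactive decay. The documents do not link lower activity to Likert points, and longer uptake changes at the same time.

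**Conclusion.** The concern holds as a gap in the analysis. Order follows booking, the second scan is always later on a single injection, and the SAP states no allowance for order. Given a common scanner effect, the overall mean estimates T + (2p − 1)g.

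The documents do not determine the size or direction of any distortion, and they do not support saying that the result is biased or that either scanner is favoured. Under the assumed values the false-positive rate runs from about 5% at an even split to about 55% at 80:20 with a 0.2-point effect and 300 pairs. The conclusion rests on additive effects, a similar scanner effect in both booking groups, and the inference that all pairs enter one test. It is worth fixing because the remedy is cheap and nothing else in the plan would let a reader judge the issue.

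**What to change.** 1. In the SAP, report for each scan order the number of patients and the mean digital-minus-standard Likert difference with its 95% CI.
2. Beside the paired t-test, report the unweighted mean of the two order-specific means with its 95% CI, using SE = (SD/2)·√(1/n1 + 1/n2), SD pooled within order, and n − 2 df. The SAP is written in the past tense, so label this post hoc if results had been seen. Compare the two estimates and their intervals, not whether one is significant and the other is not.
3. State as limitations that order followed booking; that the balanced estimate assumes a similar scanner effect in both booking groups; that a gap between the order-specific means can reflect order, different patients or different scanner models; and that scanner and order cannot be separated if nearly all pairs share one order.
4. As an editorial matter, reconcile the standard-first injection sentence in section 2.a and the 1-hour wording in section 4.c.i with the text allowing both orders.

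**Cost.** A small re-analysis with no new patients or scans. It needs scan order per patient, assumed recoverable from scan times, and uses only two means, two SDs and two counts, so the spreadsheet software named in the SAP is enough. The SE is larger than the pooled SE by 2% at 60:40, 25% at 80:20 and 67% at 90:10. If the second-scan effect is near zero, the pooled estimate is the more precise, which is why both are shown.

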3. BACKGROUND

a. Past Experimental and/or Clinical Findings

More than a decade ago, multimodality imaging was introduced into clinical routine with the development of the PET/CT. Since then, PET/CT has been widely accepted in clinical imaging and has emerged as one of the main cancer imaging modalities. With the recent development of combined PET/MRI systems for clinical use, a promising new PET detector technology using silicon photomultiplier tubes has become available. The combination of functional information delivered by highly sensitive novel PET detectors with the morphologic imaging of CT offers exciting possibilities for clinical applications as well as basic research. However, the differences between standard and digital PET detectors are fundamental. Digital PET/CT is expected to show advantages over standard PET/CT by decreasing required dose of PET radiopharmaceuticals, higher sensitivity and temporal resolution. However, as of now, only assumptions can be made about the future clinical role of digital PET/CT, as data about the performance of digital PET/CT in the clinical setting are still limited (1). We recently installed at Stanford University the first ever GE-made digital PET/CT worldwide and we plan to compare image quality with that from standard PET/CT as part of an investigator initiated research study.

b. Findings from Past Animal Experiments

Non-available.

To summarize the results of the published human studies, there were no observed adverse events to the radiopharmaceutical. The measured dosimetry showed that the critical organ with 68Ga-PSMA is the spleen, followed by the stomach wall, pancreas and bladder wall. The effective dose of 68Ga-PSMA reported (0.0236 mSv/MBq) is similar to that of 68Ga-DOTA-TOC (0.023 mSv/MBq), 68Ga-DOTA-NOC (0.025 mSv/MBq), 68Ga-DOTA-TATE (0.021 mSv/MBq) and 68Ga-NOTA-RGD (0.022 mSv/MBq).

RM2:

The first-in-human study investigated the safety, tolerability, metabolism, pharmacokinetics, biodistribution, and radiation dosimetry of 68Ga-DOTA-Bombesin (BAY 86-7548). Five healthy men underwent dynamic whole-body PET/CT after an intravenous injection of 68Ga-DOTA-Bombesin (138 ± 5 MBq). Besides total radioactivity, plasma samples were analyzed by radio-high-performance liquid chromatography for metabolism of the tracer. Dosimetry was calculated using the OLINDA/EXM software. The organs with the highest absorbed doses were the urinary bladder wall (0.62 mSv/MBq) and the pancreas (0.51 mSv/MBq). The mean effective dose was 0.051 mSv/MBq. 68Ga-DOTA-Bombesin was well tolerated by all subjects. The authors concluded that the intravenously injected 68Ga-DOTA-Bombesin is safe, and rapid metabolism is demonstrated. A 140-MBq injection of 68Ga-DOTA-Bombesin results in an effective dose of 4.76 mSv after voiding at 1 hour..

Measured human dosimetry data are available from published data (30) and presented below.

The 68Ga radioactivity was rapidly excreted through the kidneys to the urinary bladder and accumulated predominantly in the pancreas and liver. Maximum peak uptake of the total injected radioactivity was seen in the urinary bladder contents and the liver, with approximately 36% and 14%, respectively.

The mean normalized number of disintegrations in units of hours of the source organs and remainder of the body are listed in Table 1. The largest mean normalized number of disintegrations for the subjects was found in the remainder tissues (0.67 h), urinary bladder contents (0.53 h), and pancreas (0.11 h).

Organ	Mean	SD	Minimum	Maximum
Heart contents	0.038	0.0052	0.029	0.043
Kidneys	0.050	0.0071	0.041	0.060
Liver	0.074	0.014	0.055	0.093
Pancreas	0.11	0.035	0.067	0.15
Red marrow	0.087	0.030	0.066	0.11
Salivary	0.0033	0.0013	0.0011	0.0044
Spleen	0.0065	0.0014	0.0040	0.0073
Stomach wall	0.012	0.0030	0.0079	0.014
Thyroid	0.0012	0.00054	0.0057	0.0018
Urinary bladder	0.53	0.050	0.47	0.59
Remainder of body	0.67	0.071	0.59	0.75

Table 1: Normalized number of disintegrations (hours) of source organs after injection 68Ga-DOTA-Bombesin.

The estimations of the absorbed doses are reported in Table 2. The organ with the highest absorbed dose was the urinary bladder wall at 0.61 mSv/MBq, followed by the pancreas at 0.51 mSv/MBq. The mean effective dose (14) was 0.051 mSv/MBq. Thus, the effective dose from a 150-MBq injected radioactivity is 7.7 mSv, which could be reduced to roughly 5.7 mSv with frequent bladder voiding (1-h voids).

Organ	Mean	SD	Minimum	Maximum
Urinary bladder wall	0.61	0.062	0.55	0.67

Adrenals 0.011 0.00080 0.010 0.012
 Brain 0.0056 0.00051 0.0049 0.0061
 Breasts 0.0060 0.00048 0.0053 0.0064
 Gallbladder wall 0.011 0.00054 0.0099 0.011
 Lower large intestine wall 0.014 0.00036 0.013 0.014
 Small intestine 0.010 0.00032 0.0096 0.010
 Stomach wall 0.038 0.0090 0.027 0.045
 Upper large intestine wall 0.0094 0.00037 0.0089 0.0098
 Heart wall 0.028 0.0030 0.023 0.031
 Kidneys 0.081 0.011 0.067 0.096
 Liver 0.023 0.0035 0.019 0.028
 Lungs 0.0071 0.00048 0.0064 0.0076
 Muscle 0.0082 0.00038 0.0077 0.0086
 Pancreas 0.51 0.16 0.32 0.73
 Red marrow 0.013 0.0087 0.0068 0.026
 Osteogenic cells 0.013 0.0051 0.0092 0.021
 Salivary glands 0.022 0.0022 0.020 0.026
 Skin 0.0060 0.00044 0.0055 0.0065
 Spleen 0.023 0.0036 0.017 0.026
 Testes 0.010 0.00045 0.0097 0.011
 Thymus 0.0070 0.00055 0.0064 0.0076
 Thyroid 0.027 0.011 0.014 0.039
 Urinary bladder wall 0.61 0.057 0.54 0.68
 Total body 0.010 0.00031 0.0098 0.011
 Effective dose 0.051 0.0072 0.044 0.063

Table 2: Dose Equivalent estimates (mSv/MBq) after injection of 68Ga-DOTA-Bombesin

To summarize the results of the published human dosimetry study, there were no observed adverse events to the radiopharmaceutical. The measured dosimetry showed that the critical organ with 68Ga-DOTA-Bombesin is the urinary bladder, followed by the pancreas. The effective dose of 68Ga-DOTA-Bombesin reported (0.051 mSv/MBq) is approximately twice as much as that of 68Ga-DOTA-TOC (0.023 mSv/MBq), 68Ga-DOTA-NOC (0.025 mSv/MBq), 68Ga-DOTA-TATE (0.021 mSv/MBq) and 68Ga-NOTA-RGD (0.022 mSv/MBq)

c. Radiation Machines – Diagnostic Procedures

i. Examination description (well-established procedures)

Immediately after completion of the standard PET/CT the subject will undergo a study scan using the Discovery PET/CT system. Similarly, if Discovery PET/CT will be used first, scan will be acquired immediately after using standard PET/CT.

Collection of the study PET/CT imaging data shall be completed up to 1 hour after completion of the standard PET/CT scan. First a CT will be done for attenuation correction. This will be followed by emission PET scan over the same regions.

ii. Total number of times each procedure will be performed (typical study participant)

Once.

- iii. Setup and techniques to support dose modeling
 - First PET/CT: CT as ordered by referring physician, followed by emission PET
 - Second PET/CT: CT for attenuation correction, followed by emission PET
- iv. FDA status of the machine and information on dose modeling (if procedure is not well-established)

The digital PET/CT is now FDA-approved

d. Radiation Machines – Therapeutic Procedures

- i. Area treated, dose per fraction/number of fractions, performed as part of normal clinical management or due to research participation (well-established procedures)
N/A
- ii. FDA status of the machine, basis for dosimetry, area treated, dose per fraction and number of fractions (if procedure is not well-established)
N/A

5. DEVICES USED IN THE STUDY

a. IDE-Exempt Devices

IND-Exempt Device 1	
Name:	Discovery MI
Description:	Digital PET/CT scanner, that is FDA approved.

6. DRUGS, BIOLOGICS, REAGENTS, OR CHEMICALS USED IN THE STUDY

a. Investigational Drugs, Biologics, Reagents, or Chemicals

Investigational Product 1	
Name:	Ga-68 PSMA
Dosage:	3-5 mCi
Administration Route:	i.v.
Investigational Product 2	
Name:	Ga-68 RM2
Dosage:	140 MBq
Administration Route:	i.v.

b. Commercial Drugs, Biologics, Reagents, or Chemicals

Commercial Product 1	
Name:	F-18 FDG
Dosage:	10-12 mCi
Administration Route	i.v.
New and different use? (Y/N)	No
Commercial Product 2	
Name:	F-18 NaF
Dosage:	5-10 mCi
Administration Route	i.v.

New and different use? (Y/N)	No
Commercial Product 3	
Name:	Ga-68 DOTA TATE
Dosage:	5-7 mCi
Administration Route	i.v.
New and different use? (Y/N)	No

7. DISINFECTION PROCEDURES FOR MEDICAL EQUIPMENT USED ON BOTH HUMANS AND ANIMALS

N/A

8. PARTICIPANT POPULATION

a. Planned Enrollment

300 adult participants will be enrolled at Stanford. Participants will be clinical patients who are scheduled for a standard of care or research PET/CT.

b. Age, Gender, and Ethnic Background

All age ranges of adult population (> 18-years old) will be recruited. Both men and women will be recruited. All ethnic background will be recruited. No healthy volunteers will be recruited. Pregnant women will be excluded because pregnancy is a contraindication for a PET/CT study.

c. Vulnerable Populations

No potentially vulnerable patients will be entered into this study.

d. Rationale for Exclusion of Certain Populations

We are not excluding any minorities; we are not excluding women due to their gender, only if they are pregnant or breastfeeding, to protect the fetus or baby.

e. Stanford Populations

No laboratory personnel, employees, and/or students will be recruited for this protocol.

f. Healthy Volunteers

No healthy volunteers will be included into this study.

g. Recruitment Details

Potential participants will be identified from the PET/CT schedule in Nuclear Medicine (patients referred for standard or research PET/CT). Therefore a Waiver of Authorization for Recruitment will be applied for in the relevant section.

3 days+ in advance of scan, fellows/coordinators would identify patients that qualify based on data in the medical record.

2 days in advance, technologist or Nuc Med physician call patients to prep patients for the scan and ask whether a fellow/coordinator can contact them about the study.

1 day in advance, if they agree to be contacted, a fellow or coordinator would discuss the study with them.

Day of the scan, if they are still a candidate, fellow/coordinator will discuss further with them, answer questions, and sign informed consent.

h. Eligibility Criteria

i. Inclusion Criteria

- Patient is \geq 18 years old at the time of the scan
- Patient provides written informed consent
- Patient is referred for standard or research (68Ga PSMA or 68Ga RM2) PET/CT
- Patient is capable of complying with study procedures
- Patient is able to remain still for duration of imaging procedure (approximately 60 minutes total for both PET/CT)

ii. Exclusion Criteria

- Patient is $<$ 18 years old at the time of the drug administration
- Patient is pregnant or nursing

i. Screening Procedures

Patients will be identified from the PET/CT schedule in Nuclear Medicine. Therefore a Waiver of Authorization for Recruitment will be obtained in the relevant section.

j. Participation in Multiple Protocols

As part of the consent form process the patient will be asked if they are participating in a concurrent research protocol. Those enrolled in the Ga68 PSMA or Ga58 RM2 protocols will be allowed to participate.

k. Payments to Participants

Patients will be paid \$ [redacted] for participation in this study.

The second PET/CT will add up to 60 minutes to the patients' scheduled PET/CT visit. Given the construction delays and parking situation at Stanford, the investigators felt that the participants need to be compensated for their time and effort. We consider \$ [redacted] an appropriate amount given the above reasons, in line with other studies and not undue pressure on participants

l. Costs to Participants

There will be no costs for participating in this study.

m. Planned Duration of the Study

The screening part of the study will involve a phone call. This will take approximately 15 minutes. The first PET/CT will take up to 90 minutes of the subjects time. This includes 1 hour tracer uptake time and the 30 minutes scan. The second scan will take up to another 60 minutes. (iii) Analysis of the participant data may take up to 6 months.

